7.2.3. Study Day 1 (Dosing Initiation)

Patients will come to the clinic in the morning. Prior to dosing, the following assessments will be conducted:

- Confirmation of Inclusion/Exclusion Criteria
- Review of concomitant medications
- Vital signs (blood pressure, temperature, pulse and respiratory rate), and weight
- Listen to heart and lungs
- ADAS-Cog11, NPI, GDS testing and C-SSRS Since Last Visit version. If the C-SSRS indicates imminent risk for suicidality, defined as the patient positively endorsing questions 4 or 5 of the suicidal ideation section or any suicidal behavior questions, discontinue study drug and refer for appropriate care.
- Blood sample collection for clinical laboratory tests
- Plasma sample collection for SavaDx and other plasma biomarkers.
- ECG

Patients will be administered 100 mg simufilam b.i.d. 1-2 h before or after a meal.

After dose on Study Day 1, the following assessments will be conducted:

- Vital signs (blood pressure, temperature, pulse and respiratory rate) at approximately 30 min, and 1 and 2 h post-dose.
- Adverse event monitoring

Clinic personnel will monitor the patients for AEs until discharge from the clinic. Upon investigator judgment, patients will be discharged with their supply of study drug until the next visit. They will be instructed to take study drug twice daily, at least 1-2 h before or after a meal. A dose can be up to 4 h late, but if a dose is missed, the next dose should NOT be doubled.

All follow-up visits can be +/- five (5) days for flexibility. For all follow-up visits except Months 4.5, 7.5 and 10.5, patients will come to the clinic in the morning and will be instructed NOT to take their morning dose prior to coming to the clinic.

7.2.4. Follow-up Visits on Months 1, 3, 9, 13, 15, 21

Patients will return to clinic in the morning before taking their morning dose.

Within 30 min prior to dosing, the following assessments will be conducted:

- Blood sample collection for PK assessment (for Cmin Month 15 only)
- Clinical laboratory tests (blood and urine) (All visits except Month 13)
- **Plasma** sample collection (from 8 mL whole blood) for SavaDx and other plasma biomarkers (All visits **except Months 1 and 13**)

After dose, the following assessments will be conducted:

- Vital signs (blood pressure, temperature, pulse and respiratory rate), and weight
- Listen to heart and lungs
- ECG (Month 1 only)
- Adverse event monitoring
- ADAS-Cog11, NPI, GDS and C-SSRS Since Last Visit version. If the C-SSRS indicates imminent risk for suicidality, defined as the patient positively endorsing questions 4 or 5 of the suicidal ideation section or any suicidal behavior questions, discontinue study drug and refer for appropriate care.
- Saliva collection for genetic testing (Month 15 Visit only)

7.2.5. Follow-up Visit on Month 2

Patients will return to clinic in the morning before taking their morning dose.

Within 30 min prior to dosing, the following assessments will be conducted:

• Clinical laboratory tests (blood and urine)

After dose, the following assessments will be conducted:

• Vital signs (blood pressure, temperature, pulse and respiratory rate), and weight

- Listen to heart and lungs
- Adverse event monitoring
- C-SSRS Since Last Visit version. If the C-SSRS indicates imminent risk for suicidality, defined as the patient positively endorsing questions 4 or 5 of the suicidal ideation section or any suicidal behavior questions, discontinue study drug and refer for appropriate care.

7.2.6. Follow-up Visits on Months 4.5, 7.5 and 10.5

Patients will return to clinic at any time of day. The visit may be conducted by telemedicine, based on the judgement of the Investigator.

The following assessments will be conducted:

- Vital signs (blood pressure, temperature, pulse and respiratory rate), and weight
- Listen to heart and lungs
- Adverse event monitoring
- C-SSRS Since Last Visit version. If the C-SSRS indicates imminent risk for suicidality, defined as the patient positively endorsing questions 4 or 5 of the suicidal ideation section or any suicidal behavior questions, discontinue study drug and refer for appropriate care.

7.2.7. Follow-up Visits on Month 6 and 18

Patients will return to the clinic in the morning on the Month 6 Visit. Those patients undergoing a CSF draw will take their morning dose upon arrival (time of dosing to be recorded).

Patients will return to clinic in the morning before taking their morning dose.

Within 30 min prior to dosing, the following assessments will be conducted:

- Blood sample collection for PK assessment (for Cmin Month 18 only)
- Clinical laboratory tests (blood and urine)
- Plasma sample collection (from 8 mL whole blood) for SavaDx and other plasma biomarkers.

After dose, the following assessments will be conducted:

- Vital signs (blood pressure, temperature, pulse and respiratory rate), and weight
- Listen to heart and lungs

- Adverse event monitoring
- ECG
- ADAS-Cog11, NPI, GDS, and C-SSRS Since Last Visit version. If the C-SSRS indicates imminent risk for suicidality, defined as the patient positively endorsing questions 4 or 5 of the suicidal ideation section or any suicidal behavior questions, discontinue study drug and refer for appropriate care.
- CSF sample collection at Month 6 (time post-dose to be recorded) only for the first 25 patients with a baseline CSF. (The next 25 patients with a baseline CSF will have CSF drawn at Month 12). Month 18 CSF draw is OPTIONAL for patients who provided a Month 6 or Month 12 CSF and is not an option for any other patients.

7.2.8. Month 12 and 24 Follow-up Visits

Patients will return to clinic in the morning before taking their morning dose. Patients who were enrolled prior to this amendment can terminate after completing the original 12-month open-label portion or can reconsent to the randomized withdrawal and final 6-month open-label portion. Month 12 morning dose in the clinic will be from Open-Label Period 1 bottle. Month 12 evening dose will be from the Randomized Period 2 bottle.

Within 30 min prior to dosing, the following assessments will be conducted:

- Clinical laboratory tests (blood and urine)
- Plasma sample collection (from 8 mL whole blood) for SavaDx and other plasma biomarkers.

After dose, the following assessments will be conducted:

- Full physical exam
- Adverse event monitoring
- MMSE-2
- ECG
- ADAS-Cog11, NPI, GDS, and C-SSRS Since Last Visit version. If the C-SSRS indicates imminent risk for suicidality, defined as the patient positively endorsing questions 4 or 5 of the suicidal ideation section or any suicidal behavior questions, discontinue study drug and refer for appropriate care.
- CSF sample collection at Month 12 (time post-dose to be recorded) for patients with a screening CSF who did not provide a CSF sample at Month 6. For those patients who provided a Month 6 CSF, this Month 12 CSF will be OPTIONAL. After 50 patients have provided either Month 6

or Month 12 CSF, no additional patients will have CSF drawn after screening. No CSF will be drawn at Month 24.

For patients undergoing a CSF draw, CSF sample collection (5 mL) will occur 1-3 h after dosing and after the MMSE, ADAS-Cog11, NPI and GDS testing has been completed. These samples will be tested for CSF biomarkers.

Patients who complete Month 12 prior to availability of drug supply for the randomized withdrawal phase (Months 12 - 18) will be dispensed additional openlabel simufilam and will return for a Withdrawal Day 1 Visit as appropriate.

7.2.9. Withdrawal Day 1 Visit – If Needed

This additional visit is **only for patients who complete Month 12 prior to availability of drug supply for the randomized withdrawal phase** (Months 12 – 18) and who have been dispensed additional open-label simufilam while waiting. Patients will return to the clinic at any time of day for the following assessments:

• ADAS-Cog11, NPI, GDS, and C-SSRS – Since Last Visit version. If the C-SSRS indicates imminent risk for suicidality, defined as the patient positively endorsing questions 4 or 5 of the suicidal ideation section or any suicidal behavior questions, discontinue study drug and refer for appropriate care.

These patients will return to the clinic one month later for the Month 13 visit and continue with the rest of the scheduled visits.

7.3. LABORATORY ASSESSMENTS

7.3.1. Clinical Laboratory Tests

The following clinical laboratory tests will be performed at screening, Day 1 predose, and at Months 1, 2, 3, 6, 9, 12, 15, 18, 21 and 24:

- Hematology: white blood cell (WBC) count with differential, red blood cell (RBC) count, hemoglobin, hematocrit, platelet count.
- Serum Chemistry: glucose, sodium, potassium, chloride, bicarbonate, calcium, phosphate, blood urea nitrogen (BUN), total bilirubin, creatinine, cholesterol, triglycerides, albumin, globulin, total protein, uric acid, alkaline phosphatase, alanine transaminase (ALT), aspartate transaminase (AST), gamma glutamyl transpeptidase (GGT), lactose dehydrogenase (LDH).
- Urinalysis: color, specific gravity, pH, protein, sugar, ketones, occult blood, creatinine clearance calculation by Cockcroft-Gault equation (without requiring a 24-h urine collection).

7.3.3. Preparation of Plasma Samples for Pharmacokinetic Determination

At each blood collection for PK (pre-dose samples for C_{min} at Months 15 and 18 only, blood samples (4 mL) will be drawn into a Vacutainer® tube containing K₂EDTA. The tubes will be placed on ice. Within 30 min of collection, the blood will be centrifuged at approximately 1000 X G for 15 min between 4-5°C. Within 30 min of centrifuging, plasma (at least 1.5 mL) will be split into two aliquots, transferred to polypropylene tubes and stored at -20°C or below until analysis.

At the end of the study, PK samples will be shipped frozen on dry ice to: Worldwide Clinical Trials Bioanalytical Sciences, [name] for bioanalytical analysis of simufilam with a validated assay. The second set of samples will be shipped separately once receipt of the first set is confirmed.

7.3.4. Preparation of CSF samples

CSF will be collected and aliquoted into **5 ml Screw-Cap LoBind Eppendorf**® **tubes** (# 0030122356). CSF samples should be split into two aliquots of 2.5 mL. Samples will be held frozen at -70°C.

When notified by Sponsor, samples will be shipped to [name] at CUNY (address above) for biomarker analyses or another lab. Samples will be shipped frozen on dry ice (Mon – Wed).

7.3.5. Collection of Cheek Swab Saliva Samples for Genetic Testing

Saliva samples will be collected only at Month 15. Patients will refrain from eating or drinking 1 h prior to saliva collection. Each patient will be instructed to spit into a saliva collection tube. The saliva will be stored at -20°C until instructed to ship by the Sponsor.

8. EARLY DISCONTINUATION

Patients may choose to discontinue study drug or study participation at any time, for any reason, and without prejudice. Patients who discontinue may be replaced at Sponsor discretion.

The following must be completed and documented in the source documents and CRFs for all patients who discontinue the study early:

- The reason for early study discontinuation.
- Vital signs (blood pressure, temperature, pulse and respiratory rate), weight, full physical examination, clinical laboratory tests, ECG, use of concomitant medications, and adverse events) should be obtained at discharge prior to release.
- Collection of plasma for biomarkers
- MMSE-2
- ADAS-Cog11, NPI and GDS (If the patient scores above 4 on the GDS assessment, a referral for further follow-up with the patient's primary care physician or psychiatrist is required. In addition, immediately administer the C-SSRS. If the C-SSRS indicates imminent risk for suicidality, defined as the patient positively endorsing questions 4 or 5 of the suicidal ideation section or any suicidal behavior questions, immediately contact the sponsor.)

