5.2. INCLUSION CRITERIA

All patients must comply with the following Inclusion Criteria:

- 1. Informed consent form (ICF) signed by the subject or legally acceptable representative. If a legally acceptable representative signs the ICF, a notation of capacity of the subject must be noted.
- 2. Patient has a caregiver or legal representative responsible for administering the drug and recording the time.
- 3. Ages \geq 50 and \leq 85 years

- 4. Clinical diagnosis of dementia due to possible or probable AD consistent with criteria established by a workgroup of the National Institute on Aging and the Alzheimer's Disease Association.
- 5. If female, postmenopausal for at least 1 year
- 6. Patient living at home, senior residential setting, or an institutional setting without the need for continuous (i.e. 24-h) nursing care
- 7. General health status acceptable for participation in the study
- 8. Fluency (oral and written) in English or Spanish
- 9. If receiving memantine, rivastigmine, galantamine or an AChEI, receiving a stable dose for at least 3 months (90 days) before screening. If receiving donepezil, receiving any dose lower than 23 mg once daily. Multiple medications are allowed.
- 10. The patient is a non-smoker for at least 3 years.
- 11. The patient or legal representative must agree to comply with the drawing of blood samples for the PK assessments, laboratory assessments and SavaDx.
- 12. MMSE-2 score \geq 16 and \leq 26 at screening, OR if > 26, must have evidence of AD pathology such as a prior CSF total tau/A β_{42} ratio \geq 0.28, an amyloid positive PET scan or hippocampal volume loss consistent with AD.

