9. ADVERSE EVENTS/SERIOUS ADVERSE EVENTS

9.1. ADVERSE EVENTS - DEFINITION

An adverse event (AE) is any undesirable event that occurs to a subject during a study, whether or not that event is considered study drug-related. Monitoring for AEs will start at dosing. Examples include:

- Any treatment-emergent signs and symptoms (events that are marked by a change from the subject's baseline/entry status [e.g., an increase in severity or frequency of pre-existing abnormality or disorder])
- All reactions from study drug, an overdose, abuse of drug, withdrawal phenomena, sensitivity or toxicity to study drug
- Apparently unrelated illnesses
- Injury or accidents (Note: if a medical condition is known to have caused the injury or accident, the medical condition and the accident should be reported as two separate medical events [e.g., for a fall secondary to dizziness, both "dizziness" and "fall" should be recorded separately])
- Extensions or exacerbations of symptoms, subjective subject-reported events,

new clinically significant abnormalities in clinical laboratory, physiological testing or physical examination

All AEs, whether or not related to the study drug, must be fully and completely documented on the AE page of the electronic Case Report Form (eCRF) and in the subject's clinical chart.

In the event that a subject is withdrawn from the study because of an AE, it must be recorded on the eCRF as such. The subject should be followed and treated by the Investigator until the abnormal parameter or symptom has resolved or stabilized.

The Investigator must report all directly observed AEs and all spontaneously reported AEs. The Investigator will ask the subject a non-specific question (e.g., "Have you noticed anything different since your dose of the study medication?") to assess whether any AEs have been experienced since the last assessment. AEs will be identified and documented on the eCRF in appropriate medical terminology. The severity and the relationship to the study drug will be determined and reported on the CRF (see below).

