9.5. SERIOUS ADVERSE EVENTS REPORTING

The reporting of SAEs by the Sponsor to Regulatory Authorities (e.g., FDA) is a regulatory requirement.

All SAEs must be reported immediately (within 24 h of learning of the event) by telephone or notification via email through the EDC system to:

[name], MD Cassava Sciences, Inc. Email: [contact] [contact]

Do not delay reporting a suspected SAE to obtain additional information. Any additional information, if collected, can be reported to the Sponsor as a follow-up to the initial report.

A completed SAE report form must be sent within five (5) working days to the medical monitor. The Sponsor will report SAEs to the IRB and FDA as required.

In the case of a death or other SAE that has occurred within 30 days after receiving study drug, the Principal Investigator must also report such an event within 24 hours of being notified.

In the event of any SAE (other than death), the subject will be instructed to contact the study physician (Principal Investigator or designee) using the phone number provided in the ICF. All patients experiencing an SAE will be seen by a Principal Investigator or designee as soon as feasible following the report of an SAE.

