* Listen to heart and lungs ^a Patients who did not initially consent for a 2-year study should be reconsented at their next study visit.

^b Patients who have a prior amyloid PET or other confirmation of AD can bypass this baseline CSF draw

^c Only for patients with a baseline CSF. Patients with a baseline CSF have the option to do a Month 6 or 12 CSF draw. Month 18 CSF draw is an option only for patients who provided Month 6 or 12 CSF.

^d Include weight for BMI calculation

^e Drug dispensation only at Month 12

NB: Withdrawal Day 1 is only for patients who complete Month 12 prior to drug supply availability for the randomized withdrawal.

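### No safety contact is scheduled after a patient's final visit, so new deaths and SAEs in the protocol's own 30-day post-drug window reach the site only by passive notification

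*Protocol*

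**What the plan says.** - **Early discontinuation (Protocol 8).** One assessment is listed. Its safety items end with "use of concomitant medications, and adverse events) should be obtained at discharge prior to release". No later contact follows.
- **Months 12 and 24 (Protocol 7.2.8).** The morning dose is taken in clinic. AE monitoring falls under "After dose, the following assessments will be conducted". Patients enrolled before the amendment may leave at Month 12. Appendix A, footnote e, reads "Drug dispensation only at Month 12", so the Month 24 clinic dose is the last planned dose.
- **Schedules.** Neither Appendix A nor SAP Table 1 has a column after Month 24.
- **AE collection (Protocol 9.1).** "Monitoring for AEs will start at dosing". AEs are events during the study; no number of days after the last dose is given.
- **Post-drug window (Protocol 9.5).** "In the case of a death or other SAE that has occurred within 30 days after receiving study drug", the text continues, "the Principal Investigator must also report such an event within 24 hours of being notified". For SAEs other than death, "the subject will be instructed to contact the study physician (Principal Investigator or designee) using the phone number provided in the ICF".
- **Caregiver (Protocol 5.2, criterion 2).** "Patient has a caregiver or legal representative responsible for administering the drug and recording the time".
- **Analysis (SAP 4.7 and 3.2).** Treatment-emergent AEs are defined by their start only. The open-label group covers Day 1 to Month 12 and Months 18 to 24, and the randomized group covers Months 12 to 18. For the annualized rate, the period at risk ends at end of treatment, given as Month 12, or at the early termination visit. Everything on the eCRF is listed.

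**The concern.** SAP 1.3 names long-term safety and tolerability as the overall study objective, and the 30-day window is the sponsor's own. If the protocol is followed exactly, nobody asks about that window. For completers the last AE question comes on the day of the last dose. Section 9.1 counts withdrawal phenomena as AEs, and a same-day check cannot observe these after the final open-label period.

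An event in the window becomes known only if someone tells the site. For SAEs short of death, that someone is the subject, who has dementia. For a death, Section 9.5 names no one.

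What is at stake is how the CSR can be read. Without a scheduled query there is no count of patients asked, so an absence of reported deaths or SAEs after exit cannot be read as an absence of events. A late event that is notified would appear in the overall treatment-emergent summary and the listings, but after Month 24 it belongs to neither phase group.

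**Working it through.** The plan gives no figure for this point, so there is none to reproduce. The check compares the texts and then sizes the window.

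**Step 1: scheduled contacts after exit, by route**

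| Exit route | Last AE enquiry | Scheduled contact afterwards |
|---|---|---|
| Month 24 completion | Month 24, after the clinic dose (7.2.8) | None |
| Month 12 exit | Month 12, after the clinic dose (7.2.8) | None |
| Early discontinuation | At discharge (Section 8) | None |

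**Step 2: can another provision detect a new event?** Section 9.1 follows a patient withdrawn for an AE until that AE resolves or stabilizes. Section 7.1 requires work-up after a liver stop. Section 8 requires referral for a GDS score above 4. Section 9.5 requires a visit after an SAE report. Each needs an event or score that is already known, so none detects a new one.

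**Step 3: size of the window**

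Inputs from SAP 2.5 are 220 enrolled, 43 open-label dropouts and 21 who did not continue past the open-label phase. SAP 2.2 gives 1:1 randomization. All 220 are assumed dosed.

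- At most 220 − 43 − 21 = 156 entered the randomized phase, so about 156/2 = 78 per arm.
- Patient-years = n × 30/365.25.

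| Patients counted | n | Patient-years |
|---|---|---|
| All enrolled (ceiling) | 220 | 18.1 |
| Less placebo-phase exits, at most 78 | 220 − 78 = 142 | 11.7 |
| Less all 43 open-label dropouts as well | 142 − 43 = 99 | 8.1 |

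The first subtraction supposes that every placebo patient left before Month 18, already off drug. The second supposes that every open-label dropout left for an AE that was followed. Both favour the plan. The 99 who remain are the 21 who stopped at Month 12 and the 78 randomized to simufilam.

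**Step 4: what asking would add.** With zero events among n patients asked, the one-sided 95% upper bound on 30-day risk is 1 − 0.05^(1/n). For assumed n of 50, 20 and 10 this is 5.8%, 13.9% and 25.9%. With nobody reachable, a call adds nothing.

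**The case against.** The best reply is that passive surveillance is a legitimate choice and the protocol has one. Section 9.5 gives 24-hour reporting, a telephone instruction and a visit after any SAE. Section 9.1 requires spontaneous reports to be recorded and AE withdrawals to be followed. Patients on placebo in Months 12 to 18 are asked about AEs at Months 13, 15 and 18, which says more about stopping the drug than one uncontrolled call. No post-treatment endpoint is planned, and by the time SAP version 3.0 was signed in December 2023 few patients, or none, may still have been callable.

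Much of this stands. It limits the point to new events after the final visit, and it may leave only the reporting part of the remedy. It does not supply an enquiry in the 30-day window.

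Four stronger readings are tempting, and the documents do not support them.

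- **AE collection has no end.** An end is implied: the AE row of Appendix A stops at Month 24, AEs are those during the study, and the SAP phase groups finish at Month 24. Only a post-dose day count is missing.
- **Caregivers have no part in reporting.** Criterion 2 is an eligibility condition and does not limit their role. The consent pages are not available, so who is told to call, and for how long, cannot be judged.
- **The 21 Month 12 leavers alone (1.7 patient-years) are the floor.** That would require all 78 simufilam patients to be followed AE withdrawals, which nothing states.
- **Late events inflate the annualized rate.** The SAP does not say whether events outside the period at risk are counted. If they are not, the effect is nil.

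**Conclusion.** The gap is real and modest. None of the three exit routes has a scheduled safety contact after the final visit, so new deaths and SAEs in the 30-day window of Section 9.5 are ascertained passively.

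The window is at most 18.1 patient-years. It is 8.1 after the two exclusions in the working. These figures assume that all 220 were dosed, that the arms split evenly and that each patient's full 30 days went unobserved. The 8.1 is not a strict minimum: followed AE withdrawals after Month 12 are not reported and would lower it, as would any early leaver who stopped drug before the discharge assessment.

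The documents give no SAE rate, so the number of missed events cannot be estimated. A reader might infer that the safety findings as a whole are unreliable. The text does not support that, because on-treatment results are untouched and off-drug enquiry exists for the placebo arm.

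**What to change.** **Protocol 7.2.8, 8 and Appendix A.** State that collection of deaths and SAEs runs to 30 days after the last dose. Add one telephone query to patient and caregiver at that point, for completers and for early leavers who can be reached. The cost is a short amendment with IRB approval and a small workload for site staff. No visit, sample or change to dosing is needed.

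**SAP 4.7.** Show events after the last dose in a separate row, with the number of patients asked.

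**CSR.** Where calls are no longer possible, say that post-exit capture was passive. The table row and this sentence cost little and can be done even if nobody can be called.

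**Annualized rate, only if it is addressed.** First extend the period at risk from Month 12 to each patient's actual end of treatment, up to Month 24. Then count only events inside that period. Restricting the rate to the period as now written would remove completers' AEs from Months 12 to 24, which would do more harm than the gap described here.

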4. SUMMARY OF STUDY DESIGN

The first 12 months is an open-label treatment of simufilam 100 mg b.i.d. for patients who completed prior Phase 2 studies PTI-125-02 and PTI-125-03. New patients are included so that up to 200 patients are enrolled in this study. Month 12 to Month 18 is a randomized withdrawal phase; patients will be randomized to continue taking simufilam 100 mg b.i.d. or matching placebo. Month 18 to Month 24 will be an additional 6 months of open-label simufilam 100 mg b.i.d. Simufilam and placebo will be administered as coated oral tablets. Patients who were enrolled prior to this amendment can continue upon reconsenting to the randomized withdrawal and final 6-month open-label portion.

All patients will provide consent to enroll into this study. Unless patients have a prior positive amyloid PET scan, MRI showing hippocampal volume loss or other prior evidence of AD, patients will undergo a CSF draw (if all other screening criteria are met) to confirm a total tau/A β_{42} ratio ≥ 0.28 .

Patients will report to the clinic in the morning of Day 1. Prior to dosing, patients will complete the following baseline measures: ECG, vital signs, clinical labs, urinalysis, listen to heart and lungs, ADAS-Cog11, neuropsychiatric inventory (NPI), geriatric depression scale (GDS), and the C-SSRS. A blood sample will be collected for plasma-based biomarkers and genetic testing.

Patients will return to the clinic every month through Month 3 and every 1.5 months through Month 12. Visits on Months 4.5, 7.5 and 10.5 will include vital signs, listening to heart and lungs, AE monitoring, C-SSRS, and drug dispensation and accountability only and may be conducted by telemedicine, based on the judgement of the Investigator. After Month 12, visits will be on Months 13, 15, 18, 21 and 24. Patients completing Month 12 prior to availability of drug supply for the randomized withdrawal phase will continue with active treatment until drug supply is ready and therefore will have an additional "Withdrawal Day 1" visit before resuming with the Month 13 visit one month later.

PK blood samples will be obtained in the morning before dosing at return visits on Months 15 and 18.

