2.2 Study Design

All patients received simufilam 100 mg b.i.d. as coated oral tablets.

The first 12 months is an open-label treatment of simufilam 100 mg b.i.d. Month 12 to Month 18 is a RW phase in which patients who completed OL treatment are randomized (1:1) to simufilam 100 mg b.i.d. or matching placebo. Month 18 to Month 24 will be an additional 6 months of open-label simufilam 100 mg b.i.d.

Simufilam and placebo will be administered as coated oral tablets. Patients who were enrolled prior to the protocol amendment could continue upon reconsenting to the RW and final 6-month open-label portion.

All patients provided consent to enroll into this study. Patients reported to the clinic in the morning of Day 1. Prior to dosing, patients completed the following baseline measures: ADAS-Cog11, C-SSRS, ECG, vital signs, clinical labs, urinalysis, listen to heart and lungs, and MMSE. A blood sample was collected for plasma-based biomarkers.

Patients returned to the clinic every month through Month 3 and every 1.5 months through Month 12. Visits on Months 4.5, 7.5 and 10.5 included vital signs, listening to heart and lungs, AE monitoring, C-SSRS and drug dispensation and accountability only. Visits at Months 4.5, 7.5 and 10.5 could be performed by telemedicine, based on the judgement of the Investigator. Only AE-monitoring and C-SSRS assessment could be performed remotely. After Month 12, visits occurred on Months 13, 15, 18, 21 and 24. Patients completing Month 12, and who chose to continue into the RW phase of the study, prior to availability of drug supply for the RW phase continued with active treatment until drug supply was ready and therefore had an additional "Withdrawal Day 1" visit before resuming with the Month 13 visit one month later. Collection of saliva for genetic testing occurred at Month 15.

Blood draws for clinical laboratory testing and urine collection for urinalysis were performed at Day 1 and Months 1, 2, 3, 6, 9, 12, 15, 18, 21 and 24. Safety assessments of vital signs and listening to heart and lungs were conducted at Months 2, 4.5, 7.5 and 10.5 visits.

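### Protocol 8 requires the C-SSRS at early discontinuation only when GDS is above 4, although every scheduled visit gives it to all patients

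*Protocol*

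**What the plan says.** Protocol 8 introduces a list that must be completed "for all patients who discontinue the study early". It covers the reason for leaving, vital signs, weight, full physical examination, laboratory tests, ECG, concomitant medications, adverse events, plasma for biomarkers, MMSE-2, ADAS-Cog11, NPI and GDS. The C-SSRS is not an item of its own. It appears in the parenthesis attached to the GDS, which opens "If the patient scores above 4 on the GDS assessment" and goes on to require referral to a "primary care physician or psychiatrist is required. In addition, immediately administer the C-SSRS". If that C-SSRS shows imminent risk, the site is to contact the sponsor at once.

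The scheduled visits work differently. Day 1 (Protocol 7.2.3) lists the "C-SSRS Since Last Visit version. If the C-SSRS indicates imminent risk for suicidality", and the same instruction recurs in 7.2.4 to 7.2.9. In none of these sections does it depend on the GDS. When risk is imminent, the action there is to "discontinue study drug and refer for appropriate care".

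The C-SSRS row in Protocol Appendix A, and again in SAP Table 1, is marked without brackets for Day 1 and every follow-up column. Neither table has an early-termination column.

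**The concern.** Nowhere else in the protocol does a depression score decide who receives the C-SSRS. At exit it does, and no reason is given for the exception.

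What is at stake is individual safety. The version used at visits asks about the time since the previous visit. A patient who stays has each interval covered at the next visit. For a patient who leaves between visits with GDS of 4 or less, the protocol does not require the last interval to be covered by any structured suicidality questions. Exit C-SSRS data are also required only from patients who screen positive for depression, in a study whose overall objective is long-term safety (SAP 1.3).

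**Working it through.** The protocol states no figure to reproduce. The check is a visit count, a comparison of the two rules, and the longest interval since the last scheduled C-SSRS.

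**Visits with an unconditional C-SSRS, by protocol section**

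- 7.2.4: Months 1, 3, 9, 13, 15, 21 = 6
- 7.2.5: Month 2 = 1
- 7.2.6: Months 4.5, 7.5, 10.5 = 3
- 7.2.7: Months 6, 18 = 2
- 7.2.8: Months 12, 24 = 2

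Total: 6 + 1 + 3 + 2 + 2 = 14. As a cross-check, Protocol 4 gives 9 visits through Month 12 (Months 1, 2, 3, 4.5, 6, 7.5, 9, 10.5, 12) and then 5 more: "After Month 12, visits will be on Months 13, 15, 18, 21 and 24". 9 + 5 = 14. The if-needed Withdrawal Day 1 visit (7.2.9) would make 15.

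**Relation to the GDS.** At Months 2, 4.5, 7.5 and 10.5 the C-SSRS is done and the GDS is not: 4 of 14. At the other 10 both are done, with nothing linking them.

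**Reading of Protocol 8.** Taken alone, the words that introduce the C-SSRS could be read as unconditional. But they stand inside the GDS parenthesis, directly after the above-4 condition, and the list has no separate C-SSRS item. The conditional reading is the natural one, and no other section or table supplies an exit C-SSRS for everyone.

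**Longest nominal interval since the last scheduled C-SSRS.** The gaps from Day 1, in months, are 1, 1, 1, 1.5, 1.5, 1.5, 1.5, 1.5, 1.5, 1, 2, 3, 3, 3. I take a month as 30.44 days. The visit window is "All follow-up visits can be +/- five (5) days for flexibility", so an early visit followed by a late one adds 5 + 5 = 10 days.

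| Period | Nominal maximum | Days | With windows |
|---|---|---|---|
| Through Month 12 | 1.5 months | 1.5 × 30.44 = 45.7 | 55.7 |
| Months 13 to 15 | 2 months | 2 × 30.44 = 60.9 | 70.9 |
| After Month 15 | 3 months | 3 × 30.44 = 91.3 | 101.3 |

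The 3-month interval spans the second half of the randomized withdrawal phase (Months 15 to 18) and all of the final open-label phase. For patients waiting between Month 12 and Withdrawal Day 1, the documents do not state the interval.

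**The case against.** The best defense is that Protocol 8 is a two-stage screen. Everyone who leaves gets a depression scale, and anyone above 4 gets a mandatory referral and an immediate C-SSRS. In requiring referral on the GDS alone, Section 8 is stricter than 7.2. This stands as a description, but it leaves unassessed the patient with new suicidal ideation or behavior and a low GDS. The protocol does not rely on such a screen at any scheduled visit.

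A reader might infer that new suicidality would surface at exit only if the patient volunteered it or mentioned it when asked the non-specific adverse event question. The documents do not support that. Every early discontinuer also has the GDS, NPI and full physical examination and gives a reason for leaving, and Protocol 9.1 has the investigator report directly observed adverse events as well. Suicidality at entry is an exclusion, and a DSMB reviews safety. These safeguards may detect a problem, though none is a structured suicidality check.

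The intervals are maxima. They apply to someone who leaves just before the next visit, and a patient who leaves at a scheduled visit has that day's C-SSRS. The protocol accepts the same spacing for patients who stay, but their next visit covers the interval.

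Timing also counts against the point. SAP version 3.0, signed in December 2023, is for the final data and describes the later visits largely in the past tense. Few exits may remain, although the documents do not say that dosing has ended.

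**Conclusion.** The point holds as a minor gap in a safety procedure. Followed exactly, Protocol 8 leaves a patient who exits between visits with GDS of 4 or less without a required structured suicidality assessment. The last one is then nominally up to 1.5, 2 or 3 months old, depending on the phase. This rests on the conditional reading of the parenthesis. If the unconditional reading was meant, the wording is ambiguous and the same edit settles it.

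The number of patients affected cannot be determined. A reader might be tempted to use the 43 open-label dropouts in SAP 2.5, but the documents do not say how many left between visits, attended an exit assessment or scored 4 or less on the GDS. No efficacy endpoint, estimand or planned analysis depends on the exit C-SSRS. The absence of a C-SSRS summary from SAP 4.7 is a separate reporting matter and adds no weight here.

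**What to change.** In Protocol 8:

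- List the C-SSRS (Since Last Visit version) as its own item for all early discontinuers.
- Keep the GDS-above-4 referral as it is.
- For imminent risk, add referral for appropriate care alongside contacting the sponsor. At present every patient required to have the exit C-SSRS is already referred through the GDS. Once patients with GDS of 4 or less are assessed too, that is no longer so.

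For patients who do not attend, remote administration is a reasonable extension. SAP 2.2 says "Only AE-monitoring and C-SSRS assessment could be performed remotely", but in the context of telemedicine at Months 4.5, 7.5 and 10.5. A reader should not take it as already permitting remote assessment at exit, so the amendment should say so expressly.

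The cost is a few minutes per exit with a scale already in use, at an assessment already required. The change helps only exits that occur after it is made.

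**Label:** cheap improvement, minor severity.
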